**Title**

PIEB Compared to CEI Relative Efficacy and Mechanism of Efficacy: A Minimum Local Analgesic Concentration (MLAC) Study

**Funding**

None. Anesthesia Department

**Seeking funding**

No

**Specific aims and basic hypothesis**

There is limited data on the mechanism of action for short acting opioids in the presence of local anesthetic in the epidural space. The recent popularization of administering epidural local anesthetic with opioid by programmed intermittent boluses (PIEB) for labor analgesia may be preferential to the traditional continuous epidural (CEI) infusion of solution for maintenance analgesia.

The aims of the study are to first determine the relative potency of PIEB compared to CEI and secondly to determine the mechanism to explain the potential PIEB efficacy advantage. The study aims will be accomplished by utilizing a validated minimal local analgesic concentration (MLAC) study design.

**General background**

Ginosar, et al. performed a minimal local anesthetic (MLAC) study comparing intravenous fentanyl with epidural fentanyl (continuous infusion) in the setting of a continuous epidural infusion of bupivacaine for labor analgesia. These findings were suggestive of a predominately spinal mechanism of action of epidural opioids.

A recent meta-analysis by George, et al. found a local anesthetic sparing effect and improved maternal satisfaction in the setting of labor epidural analgesia with programmed intermittent boluses (PIEB) of local anesthetic and short acting opioids compared with continuous epidural infusions (CEI). This finding in favor of automated intermittent boluses of solution for the maintenance of labor analgesia has popularized the technique. It remains unclear if the advantageous effects of PIEB are from the potentially greater spread of solution associated with the bolus or the bolus administration of opioids into the epidural space enhancing a potential concentration effect across with the intrathecal space. Given that the mechanism of action of epidural opioids remains poorly characterized, the effect of bolusing epidural opioids may alter the pharmacodynamic profile.

**Preliminary unpublished data**

None. We are relying on previously published work on labor analgesia using PIEB, CEI and patient-controlled epidural analgesia (PCEA).

**Experimental design**

Pregnant women who present to Labor and Delivery for an anticipated vaginal delivery will be identified as potential participants based on inclusion/exclusion criteria and their desire for labor epidural analgesia. Once identified, interested candidates will be fully informed of the study procedures, have all

questions answered, and informed consent obtained. Pregnant participants will receive a labor epidural upon the patient's request and the epidural catheter will be initiated with 15 ml 0.125% bupivacaine with 10 mcg of sufentanil (our current standard of care loading dose).

Patients will be randomized into 1 of 4 group. Either group I or II in Study Part A and group III or IV in Study Part B in a double-blinded design. Each study part will run in parallel and independently. We have separated the study into 2 parts to clarify the methodology and aims for purposes of IRB and study design protocols.

*Study Part A:*

Group 1 Starting Concentration CEI: Bupivacaine 0.06% at 10 ml/hour + Sufentanil 5 mcg (2 ml) /hour (start at 0 mins)

Group 2 Starting Concentration PIEB: Bupivacaine 0.06% 10 ml q 60 + Sufentanil 5 mcg (2 ml) q60 (start at 30 mins)

Top-Up: 5-15ml 0.25% bupivacaine for all instances of request of additional analgesia (a current standard of care treatment option for breakthrough pain)

Bupivacaine 0.06% mg/ml in 250 ml NS bag and sufentanil 2.5 mcg/ml in 100 ml NS bag.

\*Top-up is an additional dose provided upon patient request in the setting of inadequate analgesia during labor. Bupivacaine concentration to increase or decrease by 0.01% in subsequent patient depending on success or failure of previous patient

*Study Part B:*

Group 3: CEI Bupivacaine 0.06% 10 ml/hour + PIEB Sufentanil 5 mcg (2 ml) bolus q60 mins

Group 4: PIEB: Bupivacaine 0.06% 10 ml q 60 mins + CEI Sufentanil 5 mcg (2 ml)/hr continuous infusion 0.5 mcg/ml

PIEB start at 30 mins and CEI start at 0 mins.

Top-Up: 5-15ml 0.25% bupivacaine for all instances of request of additional analgesia (a current standard of care treatment option for breakthrough pain)

Bupivacaine 0.06% mg/ml in NS; 250 ml bag.

Sufentanil bag 2.5 mcg/ml in NS; 100 ml bag.

Bupivacaine concentration to increase or decrease by 0.01% in subsequent patient depending on success or failure of previous patient. Protocol success/failure/reject in each group (which will affect the subsequent patient's dose in the randomized group) will be determined by the following criteria:

Success - No supplemental analgesia request until vaginal exam c/w 8 cm dilation or more -> 0.01% w/v reduction in subsequent participant's local anesthetic.

Failure - Supplemental analgesia request c vaginal exam c/w less than 8 cm dilatation ->0.01% w/v increase in subsequent LA infusion.

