### **Significance**

These findings will facilitate a better understanding of the mechanism of action of short acting opioids in the presence of local anesthetic in the epidural space, which have the potential of optimizing strategies to provide maintenance of labor analgesia. Part 1 of our study will determine relative potency of PIEB compared for labor analgesia to CEI using MLAC to better facilitate appropriate initial epidural pump settings and maternal dosing. Part 2 of our study will determine mechanism to explain the PIEB efficacy advantage, so that the epidural technique can be optimize.

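### Part B bolus-doses sufentanil without the bupivacaine volume and, analysed alone, gives only a difference between two delivery effects, so by itself it does not establish why combined PIEB works

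*Combined protocol and SAP*

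**What the plan says.** Under Experimental design, Part A compares "Group 1 Starting Concentration CEI: Bupivacaine 0.06% at 10 ml/hour + Sufentanil 5 mcg (2 ml) /hour (start at 0 mins" with "Group 2 Starting Concentration PIEB: Bupivacaine 0.06% 10 ml q 60 + Sufentanil 5 mcg (2 ml) q60 (start at 30 mins". Part B crosses the delivery modes: "Group 3: CEI Bupivacaine 0.06% 10 ml/hour + PIEB Sufentanil 5 mcg (2 ml) bolus q60 mins" against "Group 4: PIEB: Bupivacaine 0.06% 10 ml q 60 mins + CEI Sufentanil 5 mcg (2 ml)/hr continuous infusion 0.5 mcg/ml".

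The two drugs come from separate bags in both parts, and the sufentanil strength is the same: "Bupivacaine 0.06% mg/ml in 250 ml NS bag and sufentanil 2.5 mcg/ml in 100 ml NS bag" in Part A and "Sufentanil bag 2.5 mcg/ml in NS; 100 ml bag" in Part B. The two parts are to run in parallel and independently, and no analysis across them is described.

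The General background sets out the question. "It remains unclear if the advantageous effects of PIEB are from the potentially greater spread of solution associated with the bolus", or whether they come from giving the opioid as a bolus and so strengthening a concentration effect towards the intrathecal space. The Significance section then says: "Part 2 of our study will determine mechanism to explain the PIEB efficacy advantage".

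**The concern.** The two candidate mechanisms are the spread of the bolus and the opioid concentration effect. Spread plausibly depends on bolus volume. When one drug is bolused without the other, both the accompanying volume and possibly the opioid concentration change along with the delivery mode.

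An advantage in Group 3 might then reflect a small, concentrated opioid bolus that is not part of combined PIEB. The absence of an advantage might reflect a 2 ml bolus that spreads little. Neither result carries over directly to a regimen that boluses both drugs.

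Separately, Part B contains no group in which both drugs are infused and none in which both are bolused. Its single comparison sets one delivery effect against the other. What is at stake is the second stated aim, the mechanism. The relative-potency comparison in Part A is not affected.

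**Working it through.** **Inputs** (all from Experimental design): bupivacaine 0.06%, 10 ml per hour or per 60-minute bolus; sufentanil 5 mcg in 2 ml per hour or per 60-minute bolus; sufentanil bag 2.5 mcg/ml.

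**Reproducing the plan's figure.** 2 ml x 2.5 mcg/ml = 5 mcg, as stated. The extra strength printed for Group 4 does not fit: 2 ml x 0.5 mcg/ml = 1 mcg, and 5 mcg at 0.5 mcg/ml would need 10 ml. The figures below use 2.5 mcg/ml because the bag statements in both parts give it. That is a working assumption, not a view on which figure is right.

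**Hourly amounts.** 0.06% is 0.6 mg/ml, and 0.6 x 10 = 6 mg bupivacaine. With 5 mcg sufentanil in 2 ml, each group receives the same drug amounts in 12 ml per hour at the start. Only the delivery mode differs.

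**Bolus composition if Group 2's components go in together.**
- Group 2: 10 + 2 = 12 ml; bupivacaine 6 mg / 12 ml = 0.5 mg/ml = 0.05%; sufentanil 5 / 12 = 0.417 mcg/ml.
- Group 3: 2 ml, sufentanil 2.5 mcg/ml, no bupivacaine in the bolus.
- Group 4: 10 ml of bupivacaine at about 0.06%. For an assumed bolus duration of 1 to 10 minutes, dilution by the sufentanil infusion gives 0.0598% to 0.0581%.

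Group 3 against Group 2: sufentanil concentration 2.5 / 0.417 = 6 times; bolus volume 2 / 12 = one sixth. Group 4 against Group 2: volume 10 / 12 = 83%.

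**If Group 2's components go in one after the other.** Its two boluses are then the same 10 ml and 2 ml solutions as those of Groups 4 and 3, and the six-fold contrast disappears. The opioid bolus is still accompanied by a 10 ml bolus in Group 2 and only by a slow infusion in Group 3.

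**What each comparison estimates.** Write B for the effect on MLAC of bolusing rather than infusing bupivacaine, S for the same with sufentanil, and BS for their interaction. With Group 1 at m:
- Group 1 = m; Group 2 = m + B + S + BS; Group 3 = m + S; Group 4 = m + B.
- Part A: Group 2 - Group 1 = B + S + BS.
- Part B: Group 4 - Group 3 = B - S.

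The two Part B groups give a design matrix of rank 2 for four parameters, so neither B nor S is estimable from them. For example, B = S = 0 and B = S = -0.01% (one up-down step) both give a Part B difference of zero. A non-zero difference does not show which delivery mode helped and which did nothing or harmed.

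With all four groups the rank is 4: Group 4 - Group 1 = B; Group 3 - Group 1 = S; Group 2 - Group 3 - Group 4 + Group 1 = BS.

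**The case against.** The strongest reply is that the four groups form a complete 2x2 of delivery mode with equal hourly amounts, that patients are described as randomised to one of four groups, and that such a design can separate the two effects. This stands, and it is why a reader who infers that Part B can contribute nothing on mechanism goes too far. But the plan describes no four-group analysis, and the Significance section rests the claim on Part 2. Adding the two within-part differences would give B and S only if BS = 0. The difference between a combined bolus and its separated components is a reason not to assume that.

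It can also be said that bolusing one drug alone necessarily omits the other's volume, and that a small opioid bolus is a reasonable way to keep spread out of the opioid comparison. This is fair. The design need not change, but the caveat belongs in the conclusion.

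Nor does the plan say that Part B explains the Part A regimen in particular; the advantage is taken from the literature. But the General background describes that advantage for local anaesthetic and opioid bolused together, so the mismatch with Group 3 remains.

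Two stronger readings are tempting and not supported:
- *Part B uses different solutions.* The bags and starting strengths are the same in both parts. Only the bolus as delivered may differ, and the concentration part of that depends on simultaneous delivery in Group 2. The documents mention bags, not pumps.
- *The MLAC is misstated because 0.06% becomes 0.05% after mixing.* The plan steps the bupivacaine concentration, most naturally that of the prepared solution. The factor 10/12 is common to Groups 1 and 2, so their ratio is unchanged (for example 0.05 / 0.07 = 0.714 on either scale). Every group receives 10 ml of bupivacaine solution per hour, so mg/h is 100 times the nominal percentage throughout. Reporting in mg/h would change no planned comparison.

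**Conclusion.** The point holds as a limit on what Part B may conclude. Group 3's opioid bolus differs from the opioid component of combined PIEB in accompanying volume (none against 10 ml), whichever way Group 2's boluses are delivered. It differs six-fold in concentration only if they are simultaneous. These are the factors that the trial wants to separate. Independently of that, Group 4 against Group 3 identifies only B - S. Part B analysed on its own therefore does not deliver the mechanism that the Significance section promises.

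The volume and concentration figures assume the 2.5 mcg/ml bag and the 2 ml sufentanil volume in every group; the B - S result follows from the allocation of delivery modes alone. A four-group comparison would remove the second problem but not the first: a sufentanil bolus would still mean 2 ml alone in Group 3 and 2 ml alongside 10 ml in Group 2, and that difference would sit in S and BS.

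**What to change.** 1. In Specific aims and in Significance, limit the Part B conclusion to the relative effect of the boluses actually given in Groups 3 and 4. Do not present it as the mechanism of the combined PIEB regimen without stating the difference in volume and, where it applies, in concentration.
2. If a mechanism statement is wanted, prespecify a four-group (2x2 delivery-mode) comparison with Group 1 as reference, including the interaction, and keep the same caveat. Confirm that allocation is made across all four groups concurrently, since the text describes both randomisation to one of four and two independent parts.
3. State whether Group 2's two boluses are simultaneous or sequential.
4. Reconcile Group 4's 0.5 mcg/ml with the 2.5 mcg/ml bag and with 5 mcg in 2 ml.

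Items 1, 3 and 4 cost only wording. Item 2 adds an analysis of groups already planned. The downside is a narrower mechanism claim.

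### The Group 4 line gives sufentanil as 0.5 mcg/ml, but its own dose and volume, and both bag descriptions, give 2.5 mcg/ml

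*Combined protocol and SAP*

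**What the plan says.** All of the relevant text is in the Experimental design section of the combined protocol and SAP.

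- **Group 4 (Part B).** Bupivacaine is given by programmed bolus: "Group 4: PIEB: Bupivacaine 0.06% 10 ml q 60 mins". Sufentanil runs alongside it as a separate continuous infusion: "CEI Sufentanil 5 mcg (2 ml)/hr continuous infusion 0.5 mcg/ml".
- **Group 3 (Part B), its comparator.** The modes of delivery are swapped: "Group 3: CEI Bupivacaine 0.06% 10 ml/hour + PIEB Sufentanil 5 mcg (2 ml) bolus q60 mins". No sufentanil concentration is printed.
- **Part B preparation.** "Sufentanil bag 2.5 mcg/ml in NS; 100 ml bag".
- **Groups 1 and 2 (Part A).** Group 1 has "Sufentanil 5 mcg (2 ml) /hour (start at 0 mins" and Group 2 has "Sufentanil 5 mcg (2 ml) q60 (start at 30 mins". Neither line prints a sufentanil concentration.
- **Part A preparation.** "sufentanil 2.5 mcg/ml in 100 ml NS bag".

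Group 4 is thus the only group line with a sufentanil concentration on it. The document describes no 0.5 mcg/ml bag and no dilution step.

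**The concern.** The Group 4 line states a dose, a volume and a concentration, and the three cannot all be true. Any two fix the third, and the dose and volume given do not produce the concentration given. The line belongs to the current specification of a treatment arm, and the drug is an epidural opioid given to women in labor, so it should not contain a figure that contradicts the rest of it.

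The design also depends on these quantities. Part B is meant to explain any advantage of programmed boluses. The background section offers two candidate explanations: wider spread of the bolused solution, or bolus delivery of the opioid. Groups 3 and 4 separate these only if each receives the same hourly sufentanil and the same bupivacaine volume and starting concentration, so that the mode of delivery is what differs. An arm with a different opioid dose, or a much larger infused volume, would no longer give that contrast. It could also shift the bupivacaine up-and-down sequence from which the primary outcome, the minimum local analgesic concentration, is estimated.

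**Working it through.** **Inputs** (all from Experimental design)

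- Group 4 sufentanil: 5 mcg per hour, 2 ml per hour, printed concentration 0.5 mcg/ml.
- Group 4 bupivacaine: 10 ml every 60 minutes.
- Groups 1, 2 and 3 sufentanil: 5 mcg in 2 ml per hour or per 60 minutes.
- Sufentanil bag: 2.5 mcg/ml in both Part A and Part B.

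**Step 1. Try to reproduce the printed figure from its own line.** Concentration = dose / volume = 5 mcg / 2 ml = 2.5 mcg/ml. The printed value is 0.5 mcg/ml, so it is not reproduced. The ratio is 2.5 / 0.5 = 5.

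**Step 2. Compare with the other sufentanil maintenance figures.**

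| Source | Basis | mcg/ml |
|---|---|---|
| Groups 1, 2, 3 | 5 mcg / 2 ml | 2.5 |
| Group 4, dose and volume | 5 mcg / 2 ml | 2.5 |
| Part A bag | stated | 2.5 |
| Part B bag | stated | 2.5 |
| Group 4, end of line | stated | 0.5 |

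Only the last entry disagrees.

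**Step 3. Look for a reading under which 0.5 is right.**

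- Over the hourly bupivacaine volume alone: 5 mcg / 10 ml = 0.5 mcg/ml. This matches exactly, but only if the sufentanil is mixed into the 10 ml of bupivacaine and given with it. In Group 4 the bupivacaine is bolused, while the sufentanil is infused continuously in its own 2 ml/hr.
- Over both hourly volumes: 5 mcg / (10 + 2) ml = 0.417 mcg/ml. This does not match.

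The figure may be a remnant of a premixed regimen. That is an inference, and the finding does not depend on it.

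**Step 4. What would follow if a 0.5 mcg/ml solution were used.**

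- *Stated volume kept:* 0.5 mcg/ml × 2 ml/hr = 1 mcg/hr, against 5 mcg/hr in Group 3. The reduction is (5 − 1) / 5 = 80%.
- *Stated dose kept:* 5 mcg/hr / 0.5 mcg/ml = 10 ml/hr of sufentanil solution instead of 2. Total hourly volume would be 10 + 10 = 20 ml, against 10 + 2 = 12 ml as specified, which is 8 ml more.
- *Dose, volume and bag line followed, and 0.5 ignored:* 2.5 mcg/ml × 2 ml/hr = 5 mcg/hr. There is no effect.

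**The case against.** The strongest reply accepts the arithmetic and disputes its weight. Dose, volume and bag strength are what staff need to deliver the drug. All three are stated, and they agree. The trailing 0.5 is redundant, and nothing else in the document uses it. Each harmful scenario in the working requires staff to prepare a solution the plan does not describe, against the bag line, and also to disregard either the stated dose or the stated volume. The 1 mcg/hr and 20 ml/hr figures are therefore not estimates of harm or bias. The up-and-down rule changes only bupivacaine, and no analysis input uses the 0.5. Finally, the text was extracted from a PDF and the discrepancy is a single digit, so a misreading cannot be wholly excluded.

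Most of this stands, and it is why the point is minor. The surrounding text makes the intended value clear, the scenarios are conditional, and the statistical quantities are unaffected. The misreading point is a fair caution with nothing to support it: the line is complete and shows no sign of damage. None of this makes the printed number right. A treatment-arm specification that contradicts itself fivefold cannot be followed in full, and the reader should not have to decide which of its figures to discard.

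**Conclusion.** The concern holds. The concentration at the end of the Group 4 line is wrong as written: it should be 2.5 mcg/ml, five times the printed value. This follows from the line's own dose and volume and needs no outside information.

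The severity is minor. If the dose, volume and bag line were followed, the trial is unaffected, and nothing in the document shows otherwise. Only if 0.5 mcg/ml were actually used would Group 4 depart from Group 3, by an 80% lower sufentanil dose or by 8 ml/hr of extra volume. That would confound the Part B comparison. The conclusion assumes that the three agreeing figures express the intention and that the extracted text reproduces the source correctly.

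**What to change.** In the Group 4 line, replace 0.5 mcg/ml with 2.5 mcg/ml. Deleting the concentration would do equally well, since the Part B bag line already states it and no other group line carries one. As a precaution, confirm that the pump programming and pharmacy preparation for Group 4 correspond to 5 mcg in 2 ml per hour. Those settings are not described in the document, so this is a check and not the correction of a demonstrated fault.

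The cost is a one-figure edit to the protocol and a short check of the settings. The design, sample size and analysis need no change.

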**Reject (NC in subsequent LA epidural infusion)**

1. Pain >2 at 30 mins s/p initial LA load of 15 ml 0.125% bupivacaine with 10 mcg of sufentanil, without a bilateral T10 sensory level
2. Top-up (5-15ml 0.25% bupivacaine epidurally for all instances of request of additional analgesia) c/out pain >1 c/in 30 mins (i.e. catheter malfunction)
3. Progression to cervical dilatation >8 cm c/or delivers in 2 hrs from epidural placement (i.e. precipitous labor)
4. Progression to CS before 8 cm cervical dilatation
5. Patient request
6. Managing clinician's request
7. Changes to the maintenance regimen

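### The Failure rule has no earliest time, so an early request in Groups 2 and 4 that escapes the Reject criteria moves the concentration before any study bupivacaine is given

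*Combined protocol and SAP*

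**What the plan says.** All women first receive the same load: "the epidural catheter will be initiated with 15 ml 0.125% bupivacaine with 10 mcg of sufentanil" (Experimental design). In Study Part A, Group 1 then receives "Bupivacaine 0.06% at 10 ml/hour + Sufentanil 5 mcg (2 ml) /hour (start at 0 mins" and Group 2 receives "Bupivacaine 0.06% 10 ml q 60 + Sufentanil 5 mcg (2 ml) q60 (start at 30 mins". Study Part B states "PIEB start at 30 mins and CEI start at 0 mins". Group 4 is "PIEB: Bupivacaine 0.06% 10 ml q 60 mins + CEI Sufentanil 5 mcg (2 ml)/hr continuous infusion", and Group 3 is its mirror image, with bupivacaine infused and sufentanil given as boluses. The section does not say which event is minute 0.

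The scoring rule is "Failure - Supplemental analgesia request c vaginal exam c/w less than 8 cm dilatation ->0.01% w/v increase in subsequent LA infusion". It names no earliest time for the request.

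The Reject list leaves the next concentration unchanged. Its first item is "Pain >2 at 30 mins s/p initial LA load", and applies only if there is also no bilateral T10 level. Its second item concerns pain within 30 minutes of a top-up and is explained as catheter malfunction. Patient request, managing clinician's request and an open category for other reasons are also on the list. Rejected women get no study number and no further data collection.

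**The concern.** An up-down sequence estimates the MLAC because each woman's outcome responds to the concentration she was given. In Groups 2 and 4 the tested bupivacaine is not started until 30 minutes. A request before then cannot depend on the tested concentration, yet under the Failure rule as written it raises the next woman's concentration. Failures of this kind push the estimated MLAC up. Each one also changes what the next woman receives, so the step cannot be undone at analysis.

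The infusion arms have some study bupivacaine on board over the same half hour, so the same early request follows different exposure in different groups. Part A exists to compare PIEB with CEI on relative potency, so an unequal share of such requests between Groups 1 and 2 would enter that comparison directly.

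**Working it through.** **1. Plan figures.** The plan gives no early-request rate, no tolerance SD and no target difference, so it has no figure of its own to reproduce on this point. Its one design number is 160 patients, 80 for each study group. It comes without alpha, power, difference or SD, so it cannot be rebuilt, and it is not disputed here.

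**2. Exposure just before 30 minutes**, taking minute 0 as the loading dose (an assumption) and the starting concentration of 0.06%:

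- Load, all groups: 15 ml × 1.25 mg/ml = 18.75 mg bupivacaine.
- Infused bupivacaine: 10 ml/h × 0.5 h = 5 ml; 5 ml × 0.6 mg/ml = 3.0 mg. One 0.01% step changes this by 5 ml × 0.1 mg/ml = 0.5 mg.
- Infused sufentanil: 5 mcg/h × 0.5 h = 2.5 mcg.

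| Group | Study bupivacaine | Study sufentanil |
|---|---|---|
| 1 | 3.0 mg | 2.5 mcg |
| 2 | 0 | 0 |
| 3 | 3.0 mg | 0 |
| 4 | 0 | 2.5 mcg |

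An early request is independent of the tested concentration in Groups 2 and 4. It is nearly so in Groups 1 and 3, where study bupivacaine is 3.0/(18.75 + 3.0) = 14% of the total.

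**3. Which early requests escape Reject.** The first Reject item needs both pain above 2 and no bilateral T10 level, judged at 30 minutes. A woman in pain who has a T10 level escapes it. So may a woman topped up at 20 minutes: 5 to 15 ml at 2.5 mg/ml is 12.5 to 37.5 mg, which may bring pain to 2 or less, or establish T10, before the check. On the catheter-malfunction gloss, the second item does not apply to her if the top-up works. On its literal wording it would remove women whose top-up works and keep those whose top-up does not. Neither reading removes every early request. The remaining items are discretionary.

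**4. Shift in one arm's MLAC.** Let a share q of women be scored Failure early at any concentration, and let F be the tolerance distribution. The sequence balances where q + (1 − q)(1 − F) = 0.5, so F = 0.5/(1 − q). With normal tolerances the shift is SD × z(0.5/(1 − q)). The documents give neither q nor SD; the last two columns assume SDs of 0.01% and 0.02% w/v.

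| q | 0.5/(1 − q) | Shift, SD units | SD 0.01% | SD 0.02% |
|---|---|---|---|---|
| 2% | 0.510 | 0.026 | 0.0003% | 0.0005% |
| 5% | 0.526 | 0.066 | 0.0007% | 0.0013% |
| 10% | 0.556 | 0.140 | 0.0014% | 0.0028% |

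**5. Shift against precision.** Sequences were simulated from 0.06% in 0.01% steps, with true MLAC 0.06%, the Dixon-Massey average and 2,000 runs per setting. Arm sizes of 40 and 80 were both used, since the sample-size sentence can be read either way.

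| n per arm | SD | Shift (SE) at q = 5% | Shift (SE) at q = 10% |
|---|---|---|---|
| 40 | 0.01% | 0.0010 (0.0024) | 0.0020 (0.0028) |
| 40 | 0.02% | 0.0015 (0.0044) | 0.0033 (0.0048) |
| 80 | 0.01% | 0.0009 (0.0017) | 0.0021 (0.0019) |
| 80 | 0.02% | 0.0016 (0.0031) | 0.0033 (0.0034) |

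Entries are in % w/v. The simulated shifts run somewhat above the formula. At q = 5% the shift is about 0.3 to 0.6 of the per-arm SE; at 10% it is about 0.7 to 1.1. If the early requests leave the concentration unchanged, the simulated mean at q = 10% returns to 0.0600–0.0601%.

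**6. Between arms.** The shift depends only on q and SD. If both are equal in two arms, it cancels in the difference.

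**The case against.** A reader might infer that every early request is a Failure and that the trial is therefore biased against PIEB. The documents do not support either step. The first Reject item removes the clearest failed loads, the second removes some women on either reading, and the discretionary items may remove others. What remains is mainly an early requester with a working block, and the documents do not say how common she is. All arms share the 18.75 mg load, and an early request in an infusion arm is scored by the same rule, so the rates may be much the same.

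Nor does an early request in Group 4 reflect the load alone: she has had sufentanil from minute 0, about 5 × 20/60 = 1.7 mcg by 20 minutes. Group 3 has bupivacaine but no study sufentanil. Each Part B arm lacks one drug, so no direction follows there. In Part A, Group 2 lacks both, so an excess of early requests under PIEB is plausible, but it is not shown.

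It can also be argued that the delayed first bolus is part of the PIEB regimen, so early requests belong in its result. That is a defensible choice for comparing regimens. It does not make the step informative about concentration, and the plan does not state that choice. A sensitivity analysis counting these women as failures serves that view.

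Finally, rejecting early requesters adds exclusions after randomisation that depend on response. This objection stands and is a real cost.

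**Conclusion.** The gap is real and narrow. As written, a request before 30 minutes in Groups 2 and 4 that escapes Reject produces a 0.01% step that says nothing about the concentration under test. This rests on minute 0 being the loading dose, which the protocol leaves open.

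The size is modest: about 0.03, 0.07 or 0.14 tolerance SD in the affected arm for an assumed q of 2%, 5% or 10%. At 5% or less it is smaller than the per-arm SE, even if every such request fell in one arm. Bias in the comparison needs a between-arm difference in q (or in tolerance SD). Its direction is plausible in Part A, unestablished, and not predictable in Part B. The point is worth settling before enrolment because the rule is cheap to state and its effect on the sequence cannot be reversed later. The first Reject item already accepts the principle that a failed load should not move the concentration.

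**What to change.** In the Experimental design section and the Success, Failure and Reject criteria:

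- Define time zero.
- State that a request before the scheduled time of the first bupivacaine bolus leaves the next concentration unchanged and is scored as Reject, at the same clock time in all four groups.
- Log each such woman with her group and assigned concentration, and report the number per group. Rejects otherwise get no study number and would leave no trace.
- Add a sensitivity analysis counting these women as failures. The probit regression already planned as a back-up is a natural place for it, since it does not need an unbroken up-down sequence.
- Reconcile the wording of the second Reject item with its gloss.

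The dosing schedule is not altered. The cost is a few sentences, some women replaced, and a few more post-randomisation exclusions that depend on response, including women in the infusion groups who have already had up to 30 minutes of study solution. If early-request rates differ by group, so will these exclusions, which is why the counts and the sensitivity analysis are needed.
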